# **Translational Neuroscience Optimization of GlyT1 Inhibitor**

Principal Investigator: [name] [name]

**Purpose:** Schizophrenia is one of the leading causes of disability, principally because current treatments lack substantial efficacy for treating cognitive impairments associated with schizophrenia (CIAS). Deficits in *N*-methyl-D-aspartate (NMDA) function are thought to contribute to CIAS by interfering with the integrity of brain functional connectivity and neuroplasticity. Enhancing NMDA receptor function via the glycine site may reduce cognitive deficits. Glycine transporter-1 inhibitors (GlyT1Is) act by raising synaptic glycine levels and increasing glycine occupancy of the high-affinity (glycineB) coagonist site of NMDA-receptor (NMDA-R) thus enhancing NMDA-R function. However, with higher doses of Glyt1Is there is a plateauing and/or worsening of effects suggestive of an inverted 'U' dose response regulation of NMDA-R function. This study is designed to test the efficacy of two doses of active PF-03463275 (40 mg, 60 mg) versus placebo in combination with cognitive remediation (CR) for the treatment of CIAS.

#### Aims:

- Aim #1:To test the efficacy of treatment with two doses of PF-03463275 (40 mg or 60 mg versus placebo) combined with CR to enhance cognitive function in chronic, stable, antipsychotic treated patients with schizophrenia as measured by the composite score on the MATRICS Consensus Cognitive Battery (MCCB).
- Aim #2: To test the efficacy of treatment of 40mg or 60mg controlled release PF-03463275 BID combined with Cognitive Remediation (CR) in reducing the deficits in LTP observed in schizophrenia.

**Background:** Schizophrenia is a chronic debilitating illness with a prevalence of approximately 1% in the general population worldwide, affecting over 3.0 million individuals in the US. The World Health Organization's Global Burden of Disease 2000 ranked schizophrenia as the fifth leading cause of years lived with a disability. Cognitive deficits, for which there are currently no proven treatments, contribute significantly to disability associated with schizophrenia. As stated by Thomas Insel, there is an urgent need to develop effective treatments for cognitive impairments of schizophrenia (CIAS) (6). The purpose of the current project is to employ translational neuroscience approaches to optimally evaluate the efficacy of the glycine transporter-1 inhibitor (GlyT1I), PF-03463275, that has not been fully tested and to thereby demonstrate its potential for efficacy in treating CIAS.

patients (n=104) with schizophrenia received the glycine site agonist D-Serine or placebo and CR for 12 weeks in a double-blind randomized manner. Both interventions were well tolerated with a ~90 % completion rate (62). These results demonstrate our capacity to successfully recruit, engage and retain sufficient patients as proposed in this study, and also demonstrate the feasibility of combining pharmacotherapy with CR.

**Significance:** Schizophrenia has been ranked by the World Health Organization's Global Burden of Disease 2000 as the fifth leading cause of years lived with a disability. CIAS affect most patients with schizophrenia (52), precede the onset of illness, range from moderate to severe (53), are strongly correlated with functional outcome (54, 55) and predict disability and vocational functioning better than positive symptoms (55). While the available antipsychotic treatments address the positive symptoms of the disorder, they do not reduce cognitive deficits. In fact, there are no approved treatments for the cognitive deficits of schizophrenia. In summary, developing effective treatments for the cognitive deficits of schizophrenia will represent a significant step forward in the treatment of this major disorder

# Inclusion/Exclusion Criteria:

#### Inclusion Criteria:

- 1) Males or females 20 to 65 years of age (inclusive).
- 2) DSM-IV schizophrenia or schizoaffective disorder
- 3) Ongoing treatment with an antipsychotic except clozapine.
- 4) No changes in antipsychotics for at least 3 months.
- 5) No psychiatric hospitalizations for the past 3 months.
- 6) Genotyped to be CYP2D6 extensive metabolizer genotype.
- 7) Able to provide written informed consent.

### Exclusion Criteria:

- 1) Female subjects who are pregnant/ breastfeeding or unwilling to practice established effective contraception as determined by the investigator prior to entering the study until 30 days following the last dose of the study. Acceptable contraceptive methods for female subjects include: Double barrier contraception or a combination of a barrier contraception *and* a hormonal implant, injectable, combined oral contraceptive, or male partner who has had a vasectomy; IUD or tubal ligation.
- 2) Genotyped to be CYP2D6 poor, intermediate, or ultra-rapid metabolizers.
- 3) Current or past clinically significant or unstable medical illness (per P.I. discretion)
- 4) Current or past history of significant neurological disorder, including head trauma with loss of consciousness, history of stroke, Parkinson's disease, epilepsy disorder, conditions that lower seizure threshold, seizures of any etiology (including substance or drug withdrawal), those who were taking medications to control seizures, or those who had increased risk of seizures.
- 5) Evidence or history of significant hepatic disorder, including acute or chronic hepatitis B and acute hepatitis C
- 6) HIV+ or AIDS.
- 7) Any condition possibly affecting drug absorption (e.g. gastrectomy).
- 8) Positive urine drug screen for substances of abuse
- 9) Treatment with an investigational drug within 30 days or 5 half-lives preceding the first dose of study medication.
- 10) Clinically significant ECG abnormality (e.g., QTC interval > 450).
- 11) Concomitant treatment with medications that interfere with cognitive testing (e.g., benzodiazepine) within 12 hours before cognitive testing and cognitive remediation.
- 12) Concomitant treatment with drugs or foods that are known to interfere with the function of CYP2D6 and CYP3A4.
- 13) Aspartate aminotransferase (AST) and/or alanine aminotransferase (ALT) >2 times the upper limit of normal (ULN) at the screening visit.
- 14) Current DSM-IV Axis I diagnosis other than schizophrenia or schizoaffective disorder.
- 15) DSM-IV defined psychoactive substance dependence within 6 months of screening or substance abuse (excluding nicotine and caffeine) within 3 months prior to screening.
- 16) IQ less than or equal to 70, as determined by the Weschler Test of Adult Reading (WTAR)

- 17) Treatment with clozapine, lamotrigine or carbamazepine because these drugs may interfere with the effect of PF-03463275 on facilitating NMDA-R function.
- 18) Treatment with monoamine oxidase inhibitors within 60 days prior to screening.
- 19) Treatment of refractory schizophrenia.
- 20) Blood donation within eight weeks of the start of the study.

**Recruitment:** Subjects for both phases of this study will be recruited by advertisements in newspapers and websites such as Craigslist and flyers that will be posted at various locations at VACHS, by referral from providers and word of mouth. All advertisements and flyers will be reviewed and approved before use by the Human Subjects Subcommittee at the VACHS and the Human Investigations Committee at Yale. In the event that a subject responds to an advertisement, they will be contacting study staff. Subjects who contact the clinic will be invited in for a face-to-face meeting. Furthermore, the research team will reach out to local mental health facilities (including the Connecticut Mental Health Center) through "lunch and learns", etc. for patient referrals. A lunch and learn is a meeting that research staff schedule with clinicians and therapists at local mental health facilities where an overview of current research protocols are presented and discussed. In the event that subjects are referred from clinics or mental health facilities, research staff will require that the subjects' clinician contacts the subject first and then refers the subject to the research clinic.

The investigators and study personnel may work with the mental hygiene clinic to conduct prescreening chart reviews to determine potentially eligible subjects for this study. If a patient diagnosed with schizophrenia or schizoaffective disorder seems eligible, their primary clinician will be approached for a referral for screening. Subjects will not be contacted directly.

**Informed Consent:** Subjects who may meet entry criteria will be invited to meet with the research staff, who will fully explain details, risks and procedures as outlined in the consent form. To ensure understanding of the study, the subject will be asked questions about the study procedures and the risks associated with participation. This process generally takes about one hour. If it appears that the study subject does not fully understand the study, the Principal Investigator (PI) may decide that the subject is not suitable for participation. If the subject is still interested after all questions have been answered, he/she will be asked to sign the informed consent form. Subjects will be informed that they can decline to participate in the study without penalty and will be given the opportunity to withdraw from the study prior to analysis of their data. A copy of the consent form will be provided to all subjects.

Great care will be taken to ensure that the subject is able to give informed consent. If any concern arises that the study subject did not fully understand the study, the principal investigator may decide that the subject is not suitable for participation. This process will involve careful explanation of the consent form by a member of the research staff and a post- test to ensure understanding of the procedures and risks of the study. The subject will be required to get 75% of all questions and all the asterisked critical questions correct on a consent questionnaire in order to participate.

For patients with schizophrenia, family and/or non-research clinicians will be involved in the process when available. The patient's primary clinician i.e. non-research clinician (if applicable) will be required to assent to patient's participation. This is standard procedure for this clinic with all studies that involve patients.

**Research Design:** This is a double-blind, placebo-controlled, within subject POC study of stable patients with schizophrenia randomized to either placebo or active PF-03463275 twice daily in addition to their antipsychotic (except clozapine) for 2 dosing periods, each lasting approximately 5 weeks. Subjects will begin treatment with the study medication upon completion of all baseline procedures. The first week of each treatment will represent a lead in period to evaluate the effects of medication alone on LTP and to confirm compliance and tolerability. All subjects will receive cognitive remediation in addition to placebo/active PF-03463275 for approximately 4 weeks each study period.

Per the P.I.'s discretion, up to 14 days may be added to a treatment period to account for extenuating circumstances, such as departmental closures or scheduling conflicts, which would otherwise inhibit completion of a period within the intended 5 weeks per study period (see procedures table, Appendix: Table 1). For the aforementioned reason, if the subject does not successfully complete a study procedure, he or she may be asked to repeat said procedure, a decision that will be made at the discretion of the principal investigator.

**Screening:** Subjects will first undergo a phone screen to initially determine eligibility. Information collected during the phone screen will only be used in the event that the subject continues to participate in the study. After determining initial eligibility, research staff will provide a brief description of the research and the subject will present to the clinic for the screening procedures described below.

Part I of the screening will consist of consenting and procedures necessary for medical and psychiatric clearance (i.e., SCID, labs, EKG, physical). Part II of the screening process will consist of history verification, and testing (i.e., assessments of intelligence and cognition). However, the procedures may need to be divided differently between screening visits in cases where subjects have limited time to dedicate to the screening appointments. Screening procedures take approximately 8 hours, and may require multiple visits. Once all screening procedures have been collected, research staff as well as the principal investigator will review all relevant information and determine, based on the inclusion and exclusion criteria, if the subject will continue with the remaining study procedures. For those found ineligible, the information collected during the phone screen will be kept, with the permission of the subject.

At the screening session, the following procedures will take place:

- 1. The subject will receive a full, written explanation of study procedures and sign a consent form. The subject will be required to successfully complete a questionnaire that will help us confirm their understanding the risks of this study before participation. They will be given two attempts and they will be required to answer all questions correctly. Any questions will be answered and a physician or nurse will be available to answer any medical questions.
- 2. Subjects will receive a detailed evaluation including a medical history and a physical examination.
- **3.** A psychiatric evaluation and a Structured Clinical Interview (SCID) for DSM-IV (non-0patient) for healthy controls will be conducted.
- 4. Laboratory tests will include urine toxicology and EKG.
- **5.** A 10-mL blood sample will collected at screening for CYP2D6 genotyping into an appropriately labeled plastic EDTA tube. The whole blood will be transported to [name]'s laboratory for standard CYP2D6 analysis.
- **6.** Intelligence will be measured using the Wechsler Adult Intelligence Scale IV (WAIS-IV) and will be added as a covariate in the neuropsychological data analysis.
- 7. Handedness will be confirmed via the Edinburgh Handedness Scale
- 8. Subjects will meet with a study doctor for cognitive assessments.
- 9. Subjects will be asked to identify a collateral source of information at the beginning of the screening process (explicitly stated in the consent form) and sign a release of information providing us permission to contact the collateral. A family member, significant other, spouse is preferred. We then contact the collateral to elicit any information that might disqualify the subject or suggest risk to the subject. In instances where there are discrepancies between the information provided by the subject and that by the collateral, we usually disqualify subjects.
- **10.** Subjects will be asked to refrain from all illicit drugs, alcohol, caffeine and other medications for 1 week prior to the test days.

Randomization to PF-03463275: Subjects will be randomized to one of two doses of the glycine transporter inhibitor (GlyT1I) PF-03463275 (40 mg or 60 mg) and placebo twice daily in addition to their standing antipsychotic dose for two treatment periods each lasting approximately 5 weeks. Treatment periods will be separated by a washout period lasting approximately 3 weeks. Randomization will be stratified by antipsychotic treatment and screening performance Intelligence Quotient (WTAR estimated FSIQ 71-90 and >91). Other variables of interest e.g., cognitive test performance (MCCB composite score), BDNF genotype, BDNF levels (low, medium and high), antipsychotic dose, that cannot be stratified because of sample size limitations will be examined post-hoc. The dose of PF-03463275 has been determined based upon sub-study 1: doses that produced at least 10% occupancy and attenuation of Ketamine effects on fMRI response to a spatial working memory task will be used in Sub-Study 2.

**MCCB:** The MCCB (5) consists of 10 tests and provides standard scores and percentiles for each of seven cognitive domains. Domains assessed include: speed of processing, attention/vigilance, working memory (verbal and visual), verbal learning, visual learning, reasoning and problem solving, and social cognition. The MCCB was developed by an expert panel of researchers, under NIMH contract, as a broad yet sensitive

measure to assess cognitive change in treatment studies. The battery includes alternate test forms for repeated administrations. The MCCB will be administered at baseline and follow-ups. Change on the MCCB composite score will be calculated to assess for the overall effect of treatment, with change in specific cognitive domains including verbal and visual learning and short-term/working memory examined as exploratory analyses.

Visual LPT Paradigm: A visual LTP procedure (13, 74) will be administered as a probe of visual cortical neuroplasticity. In brief this paradigm consists of six experimental blocks, each of 2 min duration (Figure 12), administered during electroencephalographic (EEG) recording. The first two blocks serve as baselines, during which subjects complete a visual target detection task. A central fixation cross is replaced by one of two stimuli (Figure 11, panel A) at pseudorandom order with duration of 33ms and average stimulus-onset asynchrony (SOA) of 1216ms (jittered 1075-1340ms); a circular checkerboard (10.5 x 10.5cm, subtending 6° of visual angle) or blue square checkerboard (17.5 x 17.5cm, subtending 10° of visual angle) against a white background. Each block consists of 100 trials, with the circular checkerboard presented 90% (standard) and the blue square checkerboard 10% (target). Subjects are instructed to keep their dominant index finger on a response key button and to respond as quickly as possible to the blue square checkerboard. This target detection task is used to maintain alertness to the visual stimuli and target trials are not included in analysis of LTP. Baseline blocks are followed by a 2-minute period of visual high-frequency stimulation (HFS), in which the circular checkerboard is presented alone at a rate of 8.87Hz (113ms mean stimulus onset asynchrony: 1000 presentations). Subjects are instructed to fix their gaze on the centrally presented "flickering" stimuli and to relax while remaining as still as possible. This rate of high-frequency stimulation is designed to induce potentiation, analogous to the tetanizing stimuli in classic LTP procedures, and produces a prominent ~9Hz visual steady state response over posterior-occipital electrode sites. Subjects are instructed to close their eyes for a 2-minute rest period following high-frequency stimulation to allow visual after-effects to disappear. The rest period is followed by three post-test blocks, identical to the baseline blocks, beginning 2-, 4-, and 18minutes following stimulation. LTP is characterized by an increase in visual N100 ERP amplitudes evoked by the circular checkerboard stimuli from baseline to post-test blocks.

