In addition to the compensation for each in-person visit, subjects will be compensated \$5 for completing each compliance monitoring or CAROMA visit by phone. CAROMA visits will only be completed on weekdays that the research clinic is open. Subjects may earn up to \$350 dollars for completing all possible CAROMA visits.

TABLE 1:Substudy 2 Procedures																		
	Screen		eline eeks)	Period 1 (5 weeks)					Washout (3 weeks)			Follow - Up						
Week	Screen	-2	-1	0	1	2	3	4	5	6	7	8	9	10	11	12	13	14
Day		-14	-7	0	7	14	21	28	35	42	49	56	63	70	77	84	91	98
SCID	Х																	
WTAR	х																	
Psych Evaluation	х																	
Physical	Х																	
Genotyping	Х																	
Randomizat ion				х								х						
PF v Placebo				х	х	х	х	Х	х			х	х	х	х	х	х	
CR					х	х	х	х	Х				х	х	х	х	х	
PANSS				х		Х		х				х		Х		х		
SGI				х		Х		Х	Х			х		х		х	Х	
PAOFI				Х		Х		Х	Х			Х		Х		х	Х	
Movement Exam				х		х		х				х		х		х		
MCCB		Х								Х								Х
LTP				Х					Х			Х					Х	
PK				Х	Х	Х	Х	Х	Х			Х	Х	Х	Х	Х	Х	
BDNF				х														
СВС	Х			х		Х		Х				х		х		Х		
CMP	Х			х		Х		х				х		Х		Х		
ECG	х			х		Х		х				Х		Х		Х		
Utox	х	Х	Х	Х		х		Х		Х	Х	Х		Х		Х		

SCID: Structured Clinical Interview for DSM IV; WTAR: Wechsler Test of Adult Reading; CBC: Complete Blood Count; CMP: Comprehensive Metabolic Panel; ECG: Electrocardiogram; Utox: Urine Toxicology screen; CR: Cognitive Remediation; PANSS: Positive and Negative Syndrome Scale; Sensory Gating Inventory; PAOFI: Patient Assessment of Own Functioning Inventory; LTP: Long Term Potentiation; BDNF: Brain Derived Neurotrophic Factor. Per P.I. discretion, study procedures may be repeated, and the duration of participation may be extended to account for scheduling conflicts and extenuating circumstances. Thus, the number of weeks listed per period may vary.

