NCT01911676 Translational Neuroscience Optimization of GlyT1 Inhibitor

Statistical Analysis Plan 5/28/2021

Statistical Analysis Plan:

All dependent measures were assessed for normality using normal probability plots. Descriptive statistics were calculated prior to analyses. Each dependent variable was analyzed using a mixed effects model with dose (placebo, low, high), visit (pre- vs. post-drug), their interaction and period (first or second) as main effect. Interactions involving period were also assessed but were dropped from the models for parsimony. Subject was the clustering factor and the best-fitting variance-covariance structure for the repeated measures in each model was selected based on Schwartz' Bayesian Criterion. Least square means and standard errors were calculated to describe the patterns of means for each outcome. Post-hoc mean comparisons were tested to explain significant effects in the models. Additionally, for each outcome effect slices for the interaction are reported although those should be interpreted with caution when there are no significant interactions.

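### Does leaving the protocol's intelligence covariate and the randomisation strata out of the SAP model harm the Aim 1 analysis?

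*Protocol*

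**What the plan says.** Three places in the protocol deal with intelligence, and they do not use the same instrument.

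- **Screening, item 6:** "Intelligence will be measured using the Wechsler Adult Intelligence Scale IV (WAIS-IV) and will be added as a covariate in the neuropsychological data analysis".
- **Exclusion criterion 16:** "IQ less than or equal to 70, as determined by the Weschler Test of Adult Reading (WTAR").
- **Randomization to PF-03463275:** "Randomization will be stratified by antipsychotic treatment and screening performance Intelligence Quotient (WTAR estimated FSIQ 71-90 and >91").

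Table 1, the procedures table for sub-study 2, has a screening row for WTAR ("WTAR: Wechsler Test of Adult Reading") and no row for WAIS-IV.

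On the outcome, the MCCB section states "Change on the MCCB composite score will be calculated to assess for the overall effect of treatment". Table 1 places the MCCB at Weeks -2, 6 and 14.

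The SAP specifies, for all dependent variables, a "mixed effects model with dose (placebo, low, high), visit (pre- vs. post-drug), their interaction and period (first or second) as main effect", with subject as the clustering factor. The one omission it explains is this: "Interactions involving period were also assessed but were dropped from the models for parsimony".

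**The concern.** The MCCB composite is the Aim 1 outcome, so the phrase about neuropsychological analysis most naturally covers it. A covariate announced in the protocol and then absent from the SAP without comment looks like an unrecorded change of model. The SAP is dated 5/28/2021 and written in the past tense, so a reader cannot see when or why the term was left out. Usual practice is also to adjust for factors used to stratify randomisation, and the SAP includes neither of them.

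Three details make the adjusted model hard to write down as it stands:

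- the covariate is named as WAIS-IV, while everything else uses WTAR;
- the antipsychotic factor has no stated categories;
- an eligible score of 91 falls in neither IQ band.

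If the covariate mattered to the treatment contrast, leaving it out could cost precision. It would also leave room to choose between an adjusted and an unadjusted result.

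**Working it through.** The documents give no sample size, SD, effect size or power for this trial, so there is no figure of the plan's own to reproduce. The question is what an IQ term would do to the dose-by-visit contrasts.

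**Step 1: pre and post values in both periods.** Write the score of patient *i* in period *p* at visit *v* as

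Y = dose + visit + dose×visit + period + β·IQ(i) + u(i) + e,

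where u(i) is the patient's random intercept. The change within a period, post minus pre, contains β·IQ(i) − β·IQ(i) = 0 and u(i) − u(i) = 0. The dose-by-visit contrasts come from these changes, so IQ or any stratum entered as a main effect drops out.

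Generalised least squares confirms this. The assumed set-up is sequences 40-P, P-40, 60-P and P-60, 10 patients each, total variance 1 and IQ balanced across sequences. The ratio of standard errors with and without IQ is 1.000 for 40 mg vs placebo, 60 mg vs placebo and 60 vs 40 mg.

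A separate simulation assumed 40 patients, within-patient correlation 0.7 and 0, 10% or 30% dropout before period 2. Adding IQ and both strata left the dose-by-visit estimates and standard errors unchanged. At no dropout the estimates were 0.326 and 0.136, with SE 0.212, before and after.

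**Step 2: the three MCCB assessments in Table 1.** Take Week -2 as pre in period 1, Week 6 as post in period 1 and Week 14 as post in period 2. Period 2 then has no pre value of its own, and cancellation is no longer exact. Let ρ be the patient share of variance (assumed 0.6 to 0.8) and r the IQ–MCCB correlation (assumed). Adding IQ reduces the between-patient variance from ρ to ρ − r² if r is taken against the observed score, or to ρ(1 − r²) if taken against the stable patient component. Reduction in SE, active vs placebo, with r against the observed score:

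| r | ρ = 0.8 | ρ = 0.6 |
|---|---|---|
| 0.3 | 0.13% | 0.35% |
| 0.5 | 0.46% | 1.27% |
| 0.7 | 1.44% | 4.51% |

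For 60 vs 40 mg the range over all cases is 0.07% to 2.49%. With r against the stable component the ranges are 0.10% to 1.63% (active vs placebo) and 0.06% to 0.89% (60 vs 40 mg). The 4.51% cell requires IQ to explain 0.49/0.6 = 82% of stable patient variance, which is not credible.

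**Step 3: IQ predicting change itself.** This needs an IQ-by-visit term, which the protocol does not mention. For 60 vs 40 mg the ideal gain is 1 − √(1 − r²), with r now the correlation with change:

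- r = 0.1: 1 − √0.99 = 0.5%
- r = 0.2: 1 − √0.96 = 2.0%
- r = 0.3: 1 − √0.91 = 4.6%

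That formula ignores the cost of the added terms. IQ and a two-category antipsychotic factor, each with a visit interaction, use 4 degrees of freedom, or 6 with the IQ band. A simulation with all six terms (four assessments, ρ = 0.7, unstratified randomisation, all assumed) gave a 60 vs 40 mg SE about 4% larger with 20 patients and about 2% larger with 40 at r = 0.1. For active vs placebo the SE was 0 to 2% larger at r = 0.1 to 0.2.

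**Step 4: the score of 91.** For a normal distribution truncated above 70, the share scoring exactly 91 runs from 2.3% (mean 100, SD 15) to 3.5% (mean 90, SD 12). With an assumed 20 to 60 patients the expected count is 20 × 0.0228 = 0.46 to 60 × 0.0349 = 2.1. The chance of at least one, 1 − (1 − p)^N, is 0.37 to 0.88. The IQ band is not a term in the SAP model, so the effect on the fitted contrasts is nil.

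**The case for a change.** The best case for acting is that a written commitment was dropped in silence. The SAP gives parsimony as its reason for one omission and is mute on this one. Cancellation within patients is a good justification, but the SAP does not offer it. The cancellation is also incomplete: it is inexact with three MCCB values, it could differ under another covariance structure chosen by the Bayesian criterion, and it does not cover IQ predicting the size of change. An extra adjusted model on data already collected would cost little.

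Much of that is true, and the missing explanation stands. Three points limit it.

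- **The commitment is narrower than it looks.** The protocol stratifies the randomisation and says nothing about carrying the strata, or any visit interaction, into the analysis. Asking for them is a preference.
- **The source of the commitment is uncertain.** The same screening list describes a diagnostic interview for healthy controls, whom this trial's inclusion criteria do not admit, and Table 1 for sub-study 2 has WTAR only. Item 6 may have been carried over from a wider project. This is not proven, because the genotyping item in the same list does apply here.
- **The SAP is clear about what was run:** "Each dependent variable was analyzed using a mixed effects model with dose (placebo, low, high), visit (pre- vs. post-drug), their interaction and period". What is missing is the reason, not the model.

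**Conclusion.** No change to the plan is called for. The SAP model, followed exactly, gives a sound estimate of the Aim 1 contrasts without an IQ term. The precision forgone is 0% with four assessments and mostly 0.1% to 1.3% with three. The fuller set of strata and visit interactions could lose a few per cent in a small trial. No bias in the dose-by-visit contrasts is shown. These figures rest on a random-intercept covariance and on assumed values for the patient share of variance, the IQ correlations and the number of patients. A different covariance structure or partly missing visits could shift them.

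What remains is documentation. The SAP gives no reason for omitting the covariate, the intelligence instrument is named inconsistently, and the antipsychotic categories are not listed. The upper IQ band reads most naturally as a slip for 91 or above. An analyst who wanted an adjusted sensitivity model would use the score actually collected and the bands actually used at randomisation. Settling these details would help a reader but would alter no result from the SAP model.
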